# Step 2: Fit a bayesian piecewise exponential model using the default of 8 intervals – assuming piecewise constant hazards and a gamma prior outputting the survival estimates for each set of covariates into pred1 dataset.

The below estimates the survival function  $\hat{S} = (c_i | x_i, \hat{\beta})$  where  $c_i$  is the censoring time of participant  $i, x_i$  is a vector of participants covariate values observed at or prior to initiation of study treatment, and  $\hat{\beta}$  is a vector of model parameters samples from a posterior Bayesian distribution of model parameters estimated from the observed data.

CONFIDENTIAL Page 118 of 139

### Step 3: Merge the survival function estimates for each set of covariates back onto the tte input dataset, following steps b.1 to b.3 below.

- (b.1) Compute  $p_i = 1 \hat{S}(c_i|x_i, \hat{\beta})$
- (b.2) Draw a uniform random value  $u_i \sim \text{uniform}[p_i, 1]$
- (b.3) Impute the event time  $t_i^*$  as the solution of  $u_i = 1 \hat{S}(t|x_i, \hat{\beta})$ . This will ensure that the imputed event time will be greater than the censoring time (and in fact the imputed time will be sampled from the conditional survival  $\hat{S}(t|t > c_i, x_i, \hat{\beta})$ ).

Note that when delta ( $\delta$ ) is not equal to 1 replace in  $u_i = 1 - \hat{S}(t|x_i, \hat{\beta})$  in step b.3 with  $u_i = 1 - \hat{S}(t|x_i, \hat{\beta})^{\delta}$  (set delta different for each treatment group):

(b.2) will be repeated 100 times creating 100 separate datasets each of which will be used to estimate the event times per participant as follows:

```
*--- merging survival estimate back to original dataset ---;
PROC SQL;
 CREATE TABLE tte2 AS
  SELECT pred1.survival,
       tte.trtn, tte. Region1, tte.psaecol,
        tte.numpes, tte.agegr3, tte.ttpe, tte.usubjid, tte.cnsr
  FROM tte LEFT JOIN pred1
  ON pred1.trtn =tte.trtn AND pred1.region1 =tte.region1 AND
     pred1.psaecol =tte.psaecol AND pred1.numpes=tte.numpes AND
    pred1.agegr3=tte.agegr3
    pred1.ttpe =tte.ttpe;
QUIT;
*--- ensuring survival estimate presents for all rows ---;
DATA tte3 (DROP=survival);
  SET tte2;
 BY trtn region1 psaecol numpes agegr3;
 RETAIN o surv;
  IF FIRST.numpes THEN o surv=.;
 IF survival ne . THEN o surv=survival;
 ELSE IF survival =. THEN survival=o surv;
RUN;
*--- Compute failure function p=1-survival curve (separate curves for
       each set of covariates) ---;
*--- Draw a uniform random value constrained to be >p and < 1 ---;
\star--- & delta a and & delta p will be macro variables set to the delta
adjustments for Brensocatib and Placebo respectively. The entire set of
code steps 2-5 are repeated separately for each delta tipping point ---;
DATA tte4 (RENAME=ttpe =o ttpe);
  SET tte3;
```

CONFIDENTIAL Page 119 of 139

treatment\*;

```
u=RAND('uniform',p,1); *new failure rate*;
    n_surv=1-u; *new survival rate*;
RUN;
```

- \*--- merge u back to the survival function to find the time which corresponds to the new survival estimate which is always > censored one ---;
- \*--- if there isn't a record at exactly n\_surv, then we want the latest survival estimate prior to that as the survival estimate ---;

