#### 8.3.1.2. Sensitivity Analyses

The analysis of time to first PE over the 52-Week treatment period is planned to be performed under the assumption that observations that are censored prior to Week 52 are censored-at-random (CAR) and that censoring is uninformative; meaning that censoring times and event times are independent. There is no plan to impute missing event times in the main analysis.

A tipping point analysis will be used as a sensitivity analysis to examine the effect of potential departures from the CAR assumption, e.g., censored-not-at-random (CNAR), in the main analysis. Due to the inherent difficulties in identifying the missing data mechanism in practice, all missing data (i.e., censoring prior to Week 52) will be assumed CNAR, and the tipping point penalties will be applied accordingly.

As the first step, an additional penalty (delta) will be applied to the assumed hazard rates for the CNAR data. For each brensocatib dose comparison relative to placebo, the tipping point penalties (delta adjustment) will be applied in a bi-directional manner. That is, the hazard rate for the CNAR data in the brensocatib arms will be incrementally increased. This worsening outlook is quantified by a sensitivity parameter  $\delta$  interpreted as an increased hazard of PE event post-dropout, while the hazard rate for the CNAR data in the placebo arm will be incrementally decreased. This process of incrementing the penalties will continue until the respective comparison is no longer statistically significant (i.e., the Tipping Point) per the multiple testing procedure described in Section 6.3 or until the unlikely incremented/decremented hazard rate has been achieved.

As the second step, MI of the missing first PE event times under the hazard rate assumptions will be implemented using Cox model. Post study withdrawal first PE event times will be imputed conditional upon hazard rate assumptions. The process of imputing the first PE missing event times will be repeated multiple times to create 100 separate data sets. If the imputed first event times are greater than 52 weeks, the participants will be censored at Week 52.

With each increment, the 100 complete data sets will each be analyzed using the same model as for the main analysis. The analysis results for each increment will be combined using Rubin's rules (Rubin 1987).

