# Secondary Endpoint: Time to first PE – Tipping Point (Sensitivity Analysis)

NOTE: Steps 2 to 5 will be repeated varying delta (δ) for Brensocatib and Placebo. As described in step 3, &\_delta\_a and &\_delta\_p will be macro variables set to the delta adjustments for Brensocatib and Placebo respectively. Delta = 1 reflects no delta adjustment.

**Step 1:** Create a dataset named tte containing 1 row per participant and the following variables

```
usubjid participants identifier

trtn participants treatment (1=brensocatib 25mg, 2=brensocatib 10mg, 3=placebo)

region1 stratification factor: region

psaecol stratification factor: sputum sample for Pseudomonas aeruginosa at Screening Visit (1=positive or 0=negative)

numpes Stratification factor: number of prior Pes in the previous 12 months (1= <3, 0= ≥3)

agegr3 age group: adult, adolescent

ttpe Time to first pulmonary exacerbation event

cnsr Censoring flag (1=censored, 0=event); NOTE: participants with intercurrent events will be censored.
```

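### Time-to-first-PE tipping point: the written Step 3 applies delta to S(t) but not to the lower limit of the random draw, so delta is not the post-dropout hazard multiplier that the SAP defines

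*SAP*

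**What the plan says.** SAP 8.3.1.2 describes a two-directional tipping point for participants censored before Week 52. In it, "the hazard rate for the CNAR data in the brensocatib arms will be incrementally increased", and the placebo hazard is decreased. Delta is interpreted as a change in the hazard of a PE after dropout. The section adds: "Post study withdrawal first PE event times will be imputed conditional upon hazard rate assumptions".

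SAP Appendix I (Time to first PE – Tipping Point) gives the mechanics. In its introductory note, "Delta = 1 reflects no delta adjustment". Step 3 then has three parts, written here with c for the participant's censoring time and covariates omitted:

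- b.1: p = 1 − S(c)
- b.2: u is drawn uniformly on [p, 1]
- b.3: the imputed time t solves u = 1 − S(t)

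Of b.3 the SAP says: "This will ensure that the imputed event time will be greater than the censoring time". A note then replaces the b.3 equation by u = 1 − S(t)^δ when delta is not 1, with a different delta for each treatment group. The note does not mention b.1 or qualify the guarantee. A comment in the code of the same step repeats the property, describing the time sought as the one that "corresponds to the new survival estimate which is always > censored one".

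**The concern.** To multiply the hazard by delta only after dropout, the imputed time must be drawn from the conditional survival (S(t)/S(c))^δ for t > c. That requires delta in two places: the curve being inverted and the starting point of the draw. The written steps put it only in the first. The draw then starts from a point on the unadjusted curve and is read off against the adjusted one, so the two do not meet at c.

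What is at stake is the meaning of delta. SAP 8.3.1.2 says that any tipping point found will be judged clinically by the size of the delta adjustments in both arms. That judgement needs a delta of, say, 1.3 to mean a 30% higher hazard after withdrawal.

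**Working it through.** **Inputs.** Steps b.1 to b.3 and the delta note come from SAP Appendix I. The SAP gives no numerical delta grid for this endpoint and no S(c), so the values of both below are assumptions. For one illustration S(c) is built from the planning figures in SAP 3.2: placebo rate 1.2 per year, dispersion 1 and rate ratio 0.70. These give S(t) = 1/(1 + 1.2t) for placebo and 1/(1 + 0.84t) for brensocatib, with t in years.

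**The SAP's own property at δ = 1.** From b.1 and b.2, 1 − u is uniform on [0, S(c)]. Solving u = 1 − S(t) gives S(t) = 1 − u ≤ S(c), so t ≥ c. The guarantee holds.

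**δ > 1, steps as written.** Now S(t) = (1 − u)^(1/δ). The imputed time falls before c when S(t) > S(c), that is, when 1 − u > S(c)^δ. Hence

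P(t < c) = [S(c) − S(c)^δ] / S(c) = 1 − S(c)^(δ−1).

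This is above zero for any curve with 0 < S(c) < 1. The denominator is all imputed times, including those past Week 52 that SAP 8.3.1.2 then censors at Week 52.

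- S(c) = 0.80, δ = 1.5: 1 − 0.80^0.5 = 0.106, or 11%.
- S(c) = 0.80, δ = 2: 1 − 0.80 = 0.20, or 20%.

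**δ < 1, steps as written.** The largest possible S(t) is S(c)^(1/δ), which is below S(c). No time before c can arise, but no PE can be imputed until the curve has dropped to that level.

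**Illustration: censoring at week 26.** For brensocatib S(c) = 1/1.42 = 0.704 and S(52 weeks) = 1/1.84 = 0.543. For placebo S(c) = 1/1.6 = 0.625 and S(52 weeks) = 1/2.2 = 0.455. The probability of an imputed PE by week 52 is 1 − S(52)^δ/S(c) as written (zero if that is negative), and 1 − (S(52)/S(c))^δ under the stated model.

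| Arm, δ | P(t < c) as written | Earliest imputed time as written | PE by week 52, as written | PE by week 52, stated model |
|---|---|---|---|---|
| Brensocatib, 1.3 | 10.0% | week 19.2 | 0.357 | 0.286 |
| Brensocatib, 1.6 | 19.0% | week 15.2 | 0.465 | 0.339 |
| Brensocatib, 1.9 | 27.1% | week 12.5 | 0.554 | 0.389 |
| Placebo, 0.9 | 0 | week 29.7 | 0.213 | 0.249 |
| Placebo, 0.7 | 0 | week 41.5 | 0.079 | 0.200 |
| Placebo, 0.5 | 0 | week 67.6 | 0.000 | 0.147 |

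Under the stated model the earliest imputed time is week 26 in every row. A simulation with 1,000,000 draws per scenario agreed with the formulas.

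One reading of the size: a written brensocatib delta of 1.3 gives the week-52 PE probability that the stated model gives at ln(1 − 0.357)/ln(0.543/0.704) ≈ 1.7.

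**Other censoring times.** For brensocatib over δ = 1.3 to 2.0, P(t < c) runs from 5.6% to 17.4% at week 13 and from 13.6% to 38.6% at week 39.

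**The case against.** The strongest reply is that the code may already be right. In the code for Step 3, the data step `tte4` breaks off where `p` should be computed and resumes with the end of a comment about treatment. The query that builds the next dataset is also lost from the text this point rests on. What survives suggests delta could enter there:

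- The comment introducing the arm-specific delta macro variables stands directly before that data step.
- The parallel responder-imputation code, which uses no delta, computes `p` plainly at the same spot and has no treatment comment.
- The tipping-point code later sorts on `p_surv` where the responder code sorts on `o_surv`.

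This is inference, but it is fair. A reader might conclude from the formulas that the programmed grid, or any tipping delta later reported, is wrong. The documents do not support that, because the lines that would decide it are not legible here. If the code does apply delta to `p`, then b.1 disagrees with it, and the text still needs correcting.

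A second reply is that the guarantee comes before the delta note and is true at δ = 1. That stands: the sentence is not false where it is written. The gap is that the note changes b.3 alone, and the code comment carries the property into the delta setting, where it fails for δ > 1. It is also true that SAP 8.3.1.2 states the right model and that only the appendix steps depart from it.

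**Conclusion.** The written steps, followed literally, do not carry out the analysis in SAP 8.3.1.2. For δ > 1 a share 1 − S(c)^(δ−1) of imputed times lies in time already observed to be PE-free. For δ < 1 there is an artificial event-free gap after withdrawal. The algebra does not depend on the shape of the survival curve. The percentages do depend on the assumed S(c), censoring times and deltas.

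A reader might also infer that the error could make a fragile result look robust. It works the other way: too many and too early PEs on brensocatib, too few and too late on placebo. The literal version would tip at milder deltas than the stated model and so understate robustness.

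The scope is narrow. This is one sensitivity analysis of one secondary endpoint, run only if the main result is significant (SAP 6.2), and it changes only participants censored before Week 52, whose number is not given. No effect on a hazard ratio or p-value has been calculated. The main Cox analysis imputes nothing and the responder imputation uses no delta, so both are unaffected. This is a low-severity correction.

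**What to change.** In Appendix I, Step 3, state b.1 as p = 1 − S(c)^δ with the delta of the participant's arm. Keep b.2, and keep u = 1 − S(t)^δ in b.3. Then 1 − u is uniform on [0, S(c)^δ], so S(t) ≤ S(c) and t ≥ c for every delta. The conditional survival is (S(t)/S(c))^δ, the post-dropout hazard multiplier of SAP 8.3.1.2. At δ = 1 nothing changes, and the guarantee becomes true throughout.

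Then confirm that the program applies the same delta both when it computes `p` and when it matches the draw to the survival curve. A simple check on each imputed dataset is that no imputed time precedes its censoring time.

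The cost is one formula in the SAP and a check of the program. Whether any code must change depends on the lines that could not be read.

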#### PROC SQL;

```
PROC SORT DATA=tte5 (RENAME=(ttpe=pred_ttpe)) OUT=tte6;
BY trtn region1 psaecol numpes agegr3 usubjid n_surv DESCENDING p_surv;
RUN;
```

```
DATA tte7;
   SET tte6;
   BY trtn region1 psaecol numpes agegr3 usubjid n_surv DESCENDING p_surv;
   IF LAST.usubjid THEN OUTPUT;
RUN;
```

The variable pred\_ttpe is the new predicted Time to Pulmonary Exacerbation event.

Step 4: Using the original tte dataset, replace any participants censored prior to Week 52 as identified using ttpe and cnsr, with the pred\_ttpe from the above process, updating their censoring flag to be an event. Note: this will create 100 datasets separately for each delta tipping point. Each of the datasets will be analyzed using a cox proportional hazards model outputting the parameter estimate and standard error for the trtn (Active vs Placebo) comparison (for example - into pe1 to pe100).

CONFIDENTIAL Page 120 of 139

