#### 6.7.1.6. Time to First Pulmonary Exacerbation

The time to first exacerbation event confirmed through adjudication will be calculated as

```
Time to first PE (days) = CEC assessed onset date of first PE - date of reference* + 1.
```

\*For the On-Study Estimand the date of reference will be the date of randomization, while for the On-Treatment Estimand the date of reference will be the date of first IP administration (see Sections 6.4.1 and 6.7).

Participants who do not have a PE confirmed through adjudication during the 52-week treatment period or for whom the first PE is recorded beyond Week 52 visit will be censored at the date of Week 52 (or at the date of EOS for participants early discontinued from study) visit for the On-Study Estimand and at the date of last IP intake or the date of first ICE onset for the On-Treatment Estimand. Participants randomized but not treated will not be analyzed for the On-Treatment Estimand but censored at the day of randomization.

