      survival estimate prior to that as the survival estimate ---;
PROC SQL;
 CREATE TABLE tte5 as
 SELECT pred1.ttpe, pred1.survival,
       tte4.trtn, tte4.region1, tte.agegr3
        tte4.psaecol, tte4.numpes, tte4.usubjid, tte4.cnsr, tte4.p, tte4.u,
        tte4.n surv, tte4.o ttpe, tte4.o surv
```

CONFIDENTIAL Page 124 of 139

```
FROM tte4 LEFT JOIN pred1
ON pred1.trtn=tte4.trtn AND pred1.region1=tte4.region1 AND
    pred1.psaecol =tte4.psaecol AND pred1.numpes=tte4.numpes AND
    pred1.survival >= tte4.n_surv;

QUIT;

PROC SORT DATA=tte5 (RENAME=(ttpe=pred_ttpe)) OUT=tte6;
    BY trtn region1 psaecol numpes agegr3 usubjid n_surv DESCENDING o_surv;
RUN;

DATA tte7;
    SET tte6;
    BY trtn region1 psaecol numpes agegr3 usubjid n_surv DESCENDING o_surv;
    IF LAST.usubjid THEN OUTPUT;
RUN;

The variable pred_ttpe is the new predicted Time to Pulmonary Exacerbation event.
```

Step 4: Using the original tte dataset, replace any participants censored prior to Week 52 as identified using ttpe and cnsr, with the pred\_ttpe from the above process, updating their censoring flag to be an event. Participants with an imputed event which is less than Day 365 will be considered non-responders. Participants with imputed event which is >= Day 365 will be considered Responders (as we predict they would not have have a PE prior to Week 52 even if they remained on the study). Note: this will create 100 datasets. Each of the datasets will be analyzed using a logistic regression model outputting the parameter estimate and standard error for the trtn (Active vs Placebo) comparison (for example - into pe1 to pe100).

```
PROC LOGISTIC DATA=tte8;
BY _imputation_;
CLASS trtp (ref="Placebo") REGION1(ref="North America")
        numpes (ref=">=3") psaecol (ref="Negative") agegr3 (ref="Adult");
MODEL statusn = trtn region1 numpes psaecol agegr3/CLODDS=WALD ORPVALUE;
ODS OUTPUT PARAMETERESTIMATES=pes COVB=lgscovb;
RUN;
```

CONFIDENTIAL Page 125 of 139

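### In the time-to-first-PE tipping-point analysis, Appendix I Step 4 flags every imputed time as an event and omits the Week 52 censoring rule of SAP Section 8.3.1.2

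*SAP*

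**What the plan says.** SAP Section 8.3.1.2 describes the tipping-point analysis for time to first PE. Participants censored before Week 52 have a first-PE time imputed under a hazard multiplied by delta, raised for brensocatib and lowered for placebo. It then sets the rule for late times: "If the imputed first event times are greater than 52 weeks, the participants will be censored at Week 52". It refers to Appendix I for the SAS implementation.

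Appendix I builds the imputation in steps.

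- Step 3 (b.3) solves for a time on the fitted survival curve, raised to the power delta when delta is not 1. It bounds the result from below only: "This will ensure that the imputed event time will be greater than the censoring time".
- A code comment covers draws with no exact match in the tabulated curve: "then we want the latest survival estimate prior to that as the survival estimate".
- Step 4 is told to "replace any participants censored prior to Week 52 as identified using ttpe and cnsr", using the predicted time, "updating their censoring flag to be an event". The data then go to the Cox model. Week 52 is not mentioned again as an upper limit.

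The responder imputation in the same appendix has nearly the same Step 4 sentence, but adds a cut-off: "Participants with imputed event which is >= Day 365 will be considered Responders". In the main analysis (Section 6.7.1.6), participants without a confirmed PE "will be censored at the date of Week 52", or at end of study if they left early. Section 13 does not mention the difference.

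**The concern.** The two texts give different data sets. Under Section 8.3.1.2, a dropout predicted to stay PE-free through Week 52 is censored there. Under Step 4 taken literally, the same dropout counts as an event. The programmer is sent to Appendix I, so it is not safe to assume that the body text will prevail.

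This analysis runs only when the main result is statistically significant (Section 6.2), and its purpose is to show how strong a departure from censoring at random would overturn that result. Its anchor is the cell with no penalty, delta 1 in both arms, which should be consistent with the main analysis. If the anchor or the spacing of the grid is wrong, the tipping point reported no longer measures robustness to dropout.

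**Working it through.** **Inputs from the documents.** Placebo rate 1.2 per year, dispersion 1, rate ratio 0.70, 540 per arm, two-sided 0.005 per comparison (protocol Section 10.1; SAP Sections 3.1 and 3.2).

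**The plan's own figure first.** Active rate = 1.2 × 0.70 = 0.84. Variance of the log rate ratio = [(1/1.2 + 1) + (1/0.84 + 1)]/540 = 0.00745, so SE = 0.0863. Then |ln 0.70|/0.0863 = 4.13, and 4.13 − 2.81 = 1.32, giving power 90.7% against the stated 90%. The documents give no figure for the tipping-point analysis itself, so this only anchors the scenario.

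**First-PE scenario.** With dispersion 1, the PE-free share at Week 52 is 1/(1 + rate): 1/2.2 = 45.5% on placebo and 1/1.84 = 54.3% on brensocatib. Under constant hazards the hazard ratio is ln(0.543)/ln(0.455) = 0.773.

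**Simulation.** One dose against placebo, 540 per arm, 600 trials per setting. Dropout is assumed: 5% to 30%, uniform over 52 weeks. Dropouts are imputed from the fitted hazard times delta, once per trial, followed by a Cox fit. Three rules are compared:

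- A: Section 8.3.1.2, with times over 52 weeks censored at Week 52.
- B: Step 4, with the look-up ending at Week 52, so late times become events there.
- C: Step 4, with late times kept as events after Week 52.

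| Dropout | Deltas (brensocatib/placebo) | A | B | C |
|---|---|---|---|---|
| 5% | 1/1 | 0.773 | 0.781 | 0.773 |
| 10% | 1/1 | 0.773 | 0.791 | 0.773 |
| 20% | 1/1 | 0.773 | 0.807 | 0.774 |
| 30% | 1/1 | 0.774 | 0.821 | 0.773 |
| 20% | 1.5/1 | 0.805 | 0.817 | 0.850 |
| 20% | 2/1 | 0.832 | 0.825 | 0.902 |
| 20% | 2/0.5 | 0.876 | 0.839 | 1.017 |

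Mean z at 20% dropout:

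- Deltas 1/1: −2.97 (A), −2.73 (B), −3.23 (C).
- Deltas 2/0.5: −1.54 (A), −2.23 (B), +0.21 (C).

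**Why the rules differ.** At 20% dropout and delta 1, an average trial has 75.1 + 81.0 = 156.1 imputed dropouts. Of these, 49.2 + 58.7 = 107.9, about 69%, are PE-free at Week 52 under A. Step 4 turns all of them into events, against about 540 × (0.545 + 0.457) = 541 events expected with full follow-up.

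Under B, every dropout has an event by Week 52 whatever delta is. Delta can only move those events earlier, so the hazard ratio barely responds: from 1/1 to 2/0.5 it moves by 0.839 − 0.807 = 0.032, against 0.876 − 0.773 = 0.103 under A. Under C, only imputed dropouts remain at risk after Week 52. Their hazard ratio at 2/0.5 is 0.773 × 2/0.5 = 3.09, and all of them eventually have an event, so the movement is 1.017 − 0.774 = 0.243.

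**The case against.** The strongest reply is that the rule is already in the SAP. Section 8.3.1.2 states it, Appendix I supplies only technical detail, and Step 4 can be read as shorthand. That would be persuasive if Step 4 were silent on the flag. It is not silent: it says what the flag becomes, for everyone replaced. The responder algorithm needed the extra rule and states it.

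A second reply stands in part. The Step 2 code and the Step 3 join for this endpoint are not visible in the text, so where the look-up ends is not known. A reader might infer that no dropout can be PE-free at Week 52. That follows only if the tabulated curve stops there. The visible code makes this likely: the curve is merged on observed times, those times stop at the Week 52 visit, and the one join shown in full, in the responder algorithm, is "pred1.survival >= tte4.n_surv", followed by keeping the last record. But b.3 sets no upper bound, visits have a 7-day window, and the responder rule expects times at or beyond Day 365.

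A reader might also infer that the hazard ratio is always pulled toward 1. The table does not support that. With late times kept there is no bias at delta 1, and with a capped look-up the distortion runs away from 1 at large deltas.

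**Conclusion.** The contradiction between Section 8.3.1.2 and Appendix I Step 4 is real. Followed literally, Step 4 gives a wrong tipping-point grid. The direction cannot be stated in general: a capped look-up shifts the no-penalty cell toward 1 and then blunts large penalties, which can hide or delay a tipping point, while uncapped times exaggerate the penalty and can create one.

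The sizes rest on assumptions that are not in the documents: constant hazards, dropout of 5% to 30%, and uniform dropout timing. One imputation per trial is enough for mean hazard ratios but does not reproduce the p-value from 100 imputations, so the z values only compare the rules with each other. At 5% dropout the shift at delta 1 is at most 0.781 − 0.773 = 0.008; at 30% it reaches 0.821 − 0.774 = 0.047.

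The main Cox analysis and its p-value are not touched. This is a minor correction to a sensitivity analysis, worth making because that analysis exists to test robustness.

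**What to change.** In Step 4, set the time to pred_ttpe and cnsr = 0 only if the imputed time is at most 52 weeks. Otherwise, that is when the drawn survival is below the delta-adjusted predicted survival at Week 52, S(52)^delta, set the time to Week 52 and cnsr = 1. Also state that survival estimates are output at Week 52, so that the look-up can tell a late Week 52 event from a time beyond it and the delta 1 cell is consistent with the main analysis under censoring at random.

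The delta adjustment in the threshold matters, because b.3 draws on the scale S(t)^delta. A check with unadjusted S(52) at deltas 2/1 (20% dropout, 150 replicates) misclassified about 31% of imputed brensocatib dropouts. It gave a hazard ratio of 0.746 instead of 0.835, so the penalty appeared to strengthen the drug effect.

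The cost is a sentence or two in Appendix I and the matching lines of code. No data collection or main analysis changes.
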